## **Patient recruitment**

- Patients recruited via advertisements online (clinicaltrials.gov) and in the clinics in the Digestive Health Center at Stanford Healthcare as well as social media (eg. Twitter, Facebook)
- Individuals screened by research assistant to assess eligibility
- Individuals invited for an assessment conducted by a study physician
- Those wishing to proceed sign a consent form to demonstrate their informed consent.
- Inclusion criteria
  - Male and female patients >=18 years old
  - Meet Rome IV criteria for IBS for at least 6 months
    - No restrictions on type of IBS
  - English proficiency (in order to understand use of the application)
  - Patient must be on a stable regimen for IBS for at least 30 days
  - Patients must own a smartphone (iOS or Android) in order to participate in the CBT application
- Exclusion criteria
  - Laboratory or imaging evidence of an alternative explanation of patient's symptoms
  - Active gastrointestinal disease such as Crohn's disease, ulcerative colitis, history of complete colon resection, acute infection, or any disease that precludes participation in CBT application
  - Patient already undergoing cognitive behavioral therapy
  - Psychiatric hospitalization within 10 years
  - Current or past diagnosis of a major mental illness such as schizophrenia, bipolar disorder, personality disorder or substance abuse
  - Active (within the past 3 months) suicidal ideation
  - Prisoners or other detained individuals.
  - Adults unable to consent
  - Pregnant people.

## Randomization

- Random assigned to CBT vs TAU group using randomization software

## Patient visits

- Patients will be seen in clinic at weeks 0, 8 and 24. Patients will be seen either in person or via telehealth. Consent will be obtained at the initial clinic visit either online via Recap or by paper. Optional microbiome analysis samples will be self-collected by patients at weeks 0 and 8 (and possibly 24) and returned by mail or in person. Stool collection kits will be given or mailed after consent, and CBT patients instructed to begin use of the app only after the first stool collection. The physician assessment will include a safety assessment for suicidal ideation.

## Compensation

- Patients enrolled in the trial will receive a total of [REDACTED] each upon completion of the study. A [REDACTED] will be given at week 8 and week 24.

## Interventions

1. Zemedy application

a. A mobile application that enables the digital delivery of a CBT program to people with IBS. Zemedy integrates the 8-week CBT program with other in-app features – such as educational modules and health trackers, to provide an end-to-end IBS management tool. The delivery of the CBT program in itself is guided by a chatbot persona, Elle, that mimics the conversation lead by a healthcare professional in a clinical therapy setting. Educational modules on the Zemedy app range from topics on IBS causes and symptoms, to topics on relevant exercise and diet regimens. Health trackers on the Zemedy app can be used to record flare-ups, mood, and lifestyle information, allowing data to drive the extraction of meaningful patterns in IBS symptom presentation. Therefore, the Zemedy app grants IBS patients the option of and access to invaluable treatment streams.

Patients will be guided on how to onboard the app after randomization.

### Outcome assessment

- Assess outcomes at weeks 8 and 24, after randomization by randomization software

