## **Primary Endpoint**

- Change in IBS symptoms based on the IBS symptom severity score (SSS) score at week 8 compared to baseline

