## **Secondary Endpoints**

- Change in IBS symptoms based on the IBS-SSS- at week 24 compared to baseline
- Cohen Perceived Stress Questionnaire (PSQ)
  - Measures degree situation's in one's life are seen as stressful
  - Survey will be distributed at weeks 0 and 24 of the study
- Work and social adjustment scale (WSAS)
  - Measures the effect of IBS on ability to work and manage at home, participate in social and private leisure activities and maintain relationships.
  - Survey will be distributed at weeks 0 and 24 of the study
- Subject's Global Assessment of Relief (SGA)
  - Assesses global symptoms relief asking the question, "Overall, how do you feel?". Scale of -2 to +2 , from completely worse to completely better. 1–2 considered responders and 4–5 non-responders.
  - Survey will be distributed at weeks 0 and 24 of the study
- Hospital Anxiety and Depression Scale (HADS).
  - Assesses mood measured by the total distress score (<7 normal, 8-14 borderline, 15 or >15, abnormal)
  - Survey will be distributed at weeks 0, 8 and 24 of the study
- Work Productivity and activity impairment (WPAI) questionnaire
  - Assesses work productivity based on number of days taken off from work due to health
  - Survey will be distributed at weeks 0, 8 and 24 of the study
- Fecal Sampling and Microbiome analysis (optional; opt-in)
  - Assessment of any changes in gut flora (baseline vs after intervention)
  - Stool self collection will occur at weeks 0 and 8 of the study. An additional collection may occur at week 24, contingent on PI judgment.
- Adherence to intervention assessed by use of Zemedy application in the Zemedy arm
- Decreased urgent care/ER/physician appointments due to the patient's IBS
- Application is considered to be safe without adverse events such as worsening irritable bowel syndrome symptoms, hospitalizations, worsened or new mood changes

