**Table 1: Collection of Questionnaire Data**

Questionnaire	Week 0 (Day 0)	Week 4 (Day 28)	Week 8 (Day 56)	Week 24 (Day 168)
Demographic information	x			
Prior IBS Medication Usage	x			
Current medication usage	x	x	x	
IBS-SSS	x	x	x	x
PSQ	x			x
WSAS	x			x
SGA	x			x
HADS	x		x	x
WPAI	x		x	x

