#### Statistical evaluation

The statistical analyses will be done in cooperation with a statistician. The analyses will compare scores in each evaluation point between evaluation points between the intervention and the control group. Outcomes will be assessed at weeks 8 and 24 of the study. Analyses will be conducted on the full sample (intent to treat analysis).

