#### Study completion

Patients who have completed all of the IBS-SSS at weeks 0, 4, 8, and 24 will be considered completers of the study.

SCHEDULE OF ASSESSMENTS				
Protocol Activity	Week 0 Day 0*	Week 4 Day 28*	Week 8 Day 56*	Week 24 Day 168*
Informed consent	X			
Inclusion/Exclusion Screening	X			
Randomization	X			
Zemedy onboarding (if CBT)	X			
Physician Visit	X		X	X
Demographic Information	X			
Current Medications	X	X	X	
Fecal Sampling/Microbiome (opt-in)	X		X	X**
IBS-SSS	X	X	X	X
PSQ	X			X
WSAS	X			X
SGA	X			X
HADS	X		X	X
WPAI	X		X	X
Compensation			X	X

\*The study window is six days, + / - 3 days from the noted day.

\*\*Sample collection contingent on PI judgment.

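### The week-4 IBS-SSS, the only scheduled mid-treatment symptom score common to both arms, has no stated role in the efficacy analysis, although withdrawal is expected and no missing-data method is given

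*Combined protocol and SAP*

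**What the plan says.** The primary endpoint is "Change in IBS symptoms based on the IBS symptom severity score (SSS) score at week 8 compared to baseline". The only other IBS-SSS endpoint, under Secondary Endpoints, is "Change in IBS symptoms based on the IBS-SSS- at week 24 compared to baseline".

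Two further sections give the timing of outcomes. Outcome assessment has "Assess outcomes at weeks 8 and 24, after randomization by randomization software". Statistical evaluation has "Outcomes will be assessed at weeks 8 and 24 of the study", preceded by the sentence "The analyses will compare scores in each evaluation point between evaluation points between the intervention and the control group". That section also says the full sample will be analysed by intent to treat. It names no model and no method for missing scores.

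The data collection is wider. Table 1 ("Collection of Questionnaire Data") and the Schedule of Assessments both mark the IBS-SSS at weeks 0, 4, 8 and 24, with no split by arm. Study completion then gives week 4 its single stated use: "Patients who have completed all of the IBS-SSS at weeks 0, 4, 8, and 24 will be considered completers of the study".

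The Power section bases 80% power on 22 per arm and a 50-point reduction, and enrols 30 per arm to allow for withdrawal.

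**The concern.** The primary scale is measured halfway through an 8-week intervention in every patient, and then appears in no endpoint and no described analysis. For a patient who leaves between weeks 4 and 8, it is the only scheduled score on the primary scale after baseline.

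Two things are at stake. The first is precision: the week-4 scores of patients with no week-8 score say something about where they would have been at week 8, and a model can use that. The second is bias: if patients who are doing badly at week 4 are more likely to leave, and this differs by arm, then comparing only those with a week-8 score favours the arm that lost its worst patients. The week-4 score is what would allow a correction. Both matter here because the plan expects appreciable withdrawal and promises a full-sample analysis without saying how it will be achieved.

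**Working it through.** **Inputs from the protocol.** 22 per arm, 80% power, alpha 0.05, a 50-point difference, 30 per arm enrolled (Power); IBS-SSS at weeks 0, 4, 8 and 24 (Table 1, Schedule of Assessments).

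**Inputs that are assumptions.** The SD, the correlation r between week-4 and week-8 scores, and the number N4 per arm with a week-4 score. The documents give none of these.

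**1. The plan's own sample size.** It cannot be reproduced, because no SD is stated. Solving backwards with a two-sided test:
- normal approximation: SD = 50 × √(22/2) / (1.960 + 0.842) = 59.2
- t distribution: SD = 57.8

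I use about 58 for the bias in points and 59.2 for power, where it returns 80.0% at 22 per arm. If the test is one-sided, which the plan does not say, the figures are 66.7 and 65.6.

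**2. Implied withdrawal.** (30 − 22)/30 = 8/30 = 26.7%.

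**3. Precision.** When patients leave in sequence and missingness depends only on observed scores, the maximum-likelihood variance of the week-8 mean is (SD²/22) × [1 − r²(1 − 22/N4)]. The effective n per arm is therefore 22 / [1 − r²(1 − 22/N4)].

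| r | N4 | Effective n | Power for 50 points |
|---|---|---|---|
| any | 22 | 22.0 | 80.0% |
| 0.5 | 26 | 22.9 | 81.5% |
| 0.7 | 26 | 23.8 | 83.0% |
| 0.8 | 26 | 24.4 | 83.9% |
| 0.5 | 30 | 23.6 | 82.6% |
| 0.7 | 30 | 25.3 | 85.2% |
| 0.8 | 30 | 26.5 | 86.8% |

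For example, with r = 0.8 and N4 = 30: 1 − 0.64 × (1 − 22/30) = 0.829, and 22/0.829 = 26.5. The first row is the case where nobody missing week 8 has a week-4 score; there the gain is nil.

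**4. Bias.** Suppose 26 app patients have a week-4 score, the 4 with the worst scores leave, controls leave at random, and only patients with a week-8 score are analysed. Dropping the worst 4 of 26 normal values moves the mean of the remaining 22 by about 0.27 SD (simulated; the large-sample truncation formula gives 0.28). The week-8 shift is that figure × r × SD:
- r = 0.5: 0.27 × 0.5 × 58 = 7.8 points (8.1 with 0.28)
- r = 0.7: 0.27 × 0.7 × 58 = 11.0 points (11.4 with 0.28)

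That is about 8 to 11 points in the app's favour, against a 50-point target. In a simulation of 20,000 runs at r = 0.7, the bias was −10.9 points among the remaining patients and −0.1 once week 4 was used.

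**The case against.** The strongest reply is that nothing in the plan forbids using week 4. The timing sentences say when outcomes are assessed, not that other scores are thrown away, and a week-8 primary with a week-24 secondary is compatible with week 4 as an auxiliary visit in a model or an imputation. The reference to each evaluation point could even be read to include it. Part of this stands: the plan leaves the role of week 4 unwritten and does not order the data to be discarded. But the sentence that follows names only weeks 8 and 24, so the stated plan cannot be said to use week 4.

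It can also be said that the bias belongs to the missing-data gap. That is fair. The 8 to 11 points arise only if patients without a week-8 score are left out, which the plan does not say it will do, and the dropout pattern assumed is severe. With complete week-8 data the primary comparison is valid and essentially unchanged. The two gaps do share one remedy.

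A reader might infer more than the documents support:
- **That week 4 is excluded from safety review.** Secondary Endpoints lists "adverse events such as worsening irritable bowel syndrome symptoms" with no instrument, threshold or time point, and neither the interim safety analysis nor the adverse experience section names its data. The plan specifies no link to week 4; it does not rule one out.
- **That week 4 is the only symptom information during treatment.** The app's trackers can record flare-ups in the Zemedy arm, and adverse experiences are monitored throughout. Week 4 is the only scheduled mid-treatment symptom score common to both arms.
- **That 50 points is the trial's threshold for worsening.** The Power section gives it as a reduction, that is, an improvement.

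**Conclusion.** The point holds in a limited form. The week-4 IBS-SSS is collected in both arms, but its only stated use is the completer definition, while the plan expects about 27% withdrawal and gives no missing-data method.

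The likely cost in precision is modest: an effective n of 22 where about 22.9 to 26.5 per arm was available, or roughly 1.5 to 7 percentage points of power, falling to zero if those missing week 8 also lack week 4. The possible bias is the weightier concern, but it is conditional on all of the dropout and analysis assumptions in step 4. Every figure rests on an SD, a correlation and a missing-data pattern that the documents do not supply. The week-8 endpoint itself is sound. This should be corrected because the correction is cheap.

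**What to change.** In Outcome assessment and Statistical evaluation, state that IBS-SSS scores at weeks 4, 8 and 24 enter one likelihood-based repeated-measures model in all randomized patients, with terms for arm, visit, arm-by-visit and baseline IBS-SSS. Name the week-8 arm contrast as the sole primary test and the week-4 contrast as supportive, so that no further primary test is added.

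As an optional addition, summarise IBS-SSS change from baseline at week 4 by arm. If a cut-off for worsening is wanted, it must be defined and justified separately, since the protocol contains none.

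The cost is a few sentences of analysis text, with no new visits, patients or data. The downsides are one more supportive contrast to report, and reliance on the missing-at-random assumption, which should be stated.

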**Table 1: Collection of Questionnaire Data**

Questionnaire	Week 0 (Day 0)	Week 4 (Day 28)	Week 8 (Day 56)	Week 24 (Day 168)
Demographic information	x			
Prior IBS Medication Usage	x			
Current medication usage	x	x	x	
IBS-SSS	x	x	x	x
PSQ	x			x
WSAS	x			x
SGA	x			x
HADS	x		x	x
WPAI	x		x	x

### Power

We estimate that with an initial sample size of 22 participants per intervention group and 22 per control group, we will have 80% power (alpha 0.05) to detect the minimal clinically important difference on the IBS-SSS. We expect a minimum reduction in score

of 50 points, which is considered to be a considerable improvement.ix In order to account for patient withdrawal from the trial we aim to enroll 30 patients in each study group.

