## Study Overview

This is an interventional, randomized controlled study with two study arms. The study will utilize Zemedy which provides digital delivery of a CBT program to people with IBS, via a smartphone application.

The study will involve a minimum of 44 individuals (randomized 22 in study group and 22 in the control group) with irritable bowel syndrome, who will take part in the intervention for 8 weeks. The study group will receive treatment as usual (TAU) + Zemedy intervention and the control group will receive TAU. TAU for IBS is tailored to the patient and may involve dietary modification, exercise, antispasmodic medication, laxative therapy, anti-diarrheal therapy, and pain medication. Patients will be evaluated in clinic or via telehealth at the beginning of the study, and at weeks 8 and 24. Patients can contact the physician electronically via the MyHealth application in between visits.

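### Does the Power section's 80% claim need correcting because no SD, test or sidedness is given?

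*Combined protocol and SAP*

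**What the plan says.** The Power section takes 22 participants in each arm and states that "we will have 80% power (alpha 0.05) to detect the minimal clinically important difference on the IBS-SSS". The text continues: "We expect a minimum reduction in score" and then "of 50 points, which is considered to be a considerable improvement", with a literature reference for the 50 points. To allow for withdrawal, the aim is to enrol 30 per arm. Study Overview gives the matching floor of 44 patients, 22 per arm.

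The primary endpoint is "Change in IBS symptoms based on the IBS symptom severity score (SSS) score at week 8 compared to baseline". The Statistical evaluation section says: "The analyses will compare scores in each evaluation point between evaluation points between the intervention and the control group", on the full sample by intention to treat. It names no test or model. Nowhere do the documents give an SD, a standardised effect, a baseline-to-follow-up correlation or the sidedness of the 0.05.

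**The concern.** Power for comparing two means needs a between-arm difference, an SD, a test and its sidedness. The plan supplies the sample size, alpha and the power, so the reader cannot get from the inputs to the 80%.

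The effect is also loosely worded. The important difference has no number in its own sentence, and the 50 points that follows is called a reduction in score. That could mean the improvement in the app arm alone. The app-arm reduction equals the between-arm difference only if the treatment-as-usual (TAU) arm does not change on average. TAU is not inert: "TAU for IBS is tailored to the patient and may involve dietary modification, exercise, antispasmodic medication".

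This paragraph is the plan's only justification of its size. If the true SD were well above what the authors had in mind, the trial could be too small for a 50-point difference, and a null result would be hard to interpret.

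**Working it through.** **Inputs from the documents.** n = 22 per arm, alpha = 0.05, power = 80%, 50 points (all Power section). The comparison is intervention against control (Statistical evaluation). Every SD and TAU change below is an assumption, because the plan gives none.

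**Step 1: can the 80% be reproduced?** Not forwards, since the SD is missing. The calculation can be inverted to find the SD at which the claim is true, taking 50 points as the between-arm difference.

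- Normal approximation, two-sided: SD = 50 / [(1.960 + 0.842) × √(2/22)] = 50 / (2.802 × 0.3015) = 59.2.
- Normal approximation, one-sided: SD = 50 / [(1.645 + 0.842) × 0.3015] = 66.7.
- Noncentral t, two-sided: the standardised difference giving 80% at 22 per arm is 0.8646, so SD = 50 / 0.8646 = 57.8.
- Noncentral t, one-sided: 50 / 0.7621 = 65.6.

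The 80% is therefore correct for an SD of about 58 or less (two-sided t-test), or about 66 or less (one-sided).

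**Step 2: what if the SD is something else?** Two-sided t-test, 50-point between-arm difference, complete data. The detectable difference is 0.8646 × SD.

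| Assumed SD | Power, 22 per arm | Power, 30 per arm, no loss | n per arm for 80% | Detectable difference, 22 per arm |
|---|---|---|---|---|
| 50 | 90% | 97% | 17 | 43 |
| 60 | 77% | 89% | 24 | 52 |
| 70 | 64% | 78% | 32 | 61 |
| 80 | 53% | 66% | 42 | 69 |
| 100 | 37% | 48% | 64 | 86 |

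With 30 per arm and no loss, the standardised difference for 80% is 0.7356, so the claim holds up to an SD of 50 / 0.7356 = 68.0. The plan's claim falls inside the table's range, and nothing in the documents says which row applies.

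**Step 3: which difference is the 50 points?** The Power section sizes an intervention group and a control group, and the Statistical evaluation section compares those two groups. The 50 points stands directly after the sentence on the important difference, and no other number there could be the powered effect. Between-arm is the natural reading. A within-arm paired calculation would not have needed a control-group size.

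To show the effect of the other reading, take SD 57.8 and let the 50 points be the app-arm reduction. If TAU improves by 5 points, the difference is 50 − 5 = 45 and power is 71%. If TAU improves by 10, the difference is 40 and power is 61%. These figures stack two assumptions, since the SD was chosen to return exactly 80% when TAU does not change. The entry rule also limits TAU drift: "Patient must be on a stable regimen for IBS for at least 30 days".

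**Step 4: do the sample-size figures disagree?** No. The 22 per arm is the number powered and 30 is the enrolment aim. The margin allows for a loss of 8/30 = 26.7%, and the floor of 2 × 22 = 44 in Study Overview agrees with it.

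**Step 5: what would follow from stating the inputs?** The primary endpoint, the between-arm comparison, the intention-to-treat sample, the floor of 44 and the aim of 30 per arm would all stand as written. The power statement does not enter the analysis.

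**The case for a change.** The strongest case for acting is that a sample-size claim which cannot be checked justifies nothing. Under some plausible-looking SDs the shortfall is large: at an assumed SD of 80, power is 53% with 22 per arm, and even the full 30 per arm gives only 66%. The text to add would be short, and it would tell a later reader whether a null result meant no effect or too few patients.

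Part of this stands. The SD, test and sidedness really are absent, no redaction accounts for it, and a fuller plan would have given them. But the shortfall is conditional on SDs that come from outside the documents. Most of the values tabulated lie above the 57.8 break-even; at SD 50 the same 22 per arm gives 90% and 17 would do. The cited reference for the 50 points cannot be consulted here, so it cannot settle how that figure was meant. Nor would the missing sentence settle how to interpret a null result, because that rests on the observed difference and its standard error, which come from the trial's own data.

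**Conclusion.** No change to the plan follows. The 80% is unverifiable, but it is not shown to be wrong. It is true for a 50-point between-arm difference if the SD of the analysed score is about 58 or less (two-sided t-test) or about 66 or less (one-sided), and it fails above that. The documents contain nothing that places the SD on either side.

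The wording around the 50 points is loose, but its position, the sizing of two arms and the planned comparison lead to one sensible reading. What remains is a minor reporting gap: following the plan as written would give the same estimate and the same conclusion whether or not the inputs had been recorded.

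This rests on reading the 50 points as between-arm, on a two-sample t-test with complete data at 22 per arm, and on treating every SD and TAU change above as illustrative.

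### The full-sample week-8 comparison has no rule for patients without a week-8 IBS-SSS, and as described it leaves the scheduled baseline and week-4 scores unused for adjustment

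*Combined protocol and SAP*

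**What the plan says.** - **Primary Endpoint:** "Change in IBS symptoms based on the IBS symptom severity score (SSS) score at week 8 compared to baseline".
- **Power:** the calculation is made for 22 patients in each arm, and its claim for that number is: "we will have 80% power (alpha 0.05) to detect the minimal clinically important difference on the IBS-SSS". The expected minimum reduction is put at a figure "of 50 points, which is considered to be a considerable improvement". No SD, test, sidedness or withdrawal rate is given. The section then adds: "In order to account for patient withdrawal from the trial we aim to enroll 30 patients in each study group".
- **Statistical evaluation:** "The analyses will compare scores in each evaluation point between evaluation points between the intervention and the control group". It continues: "Analyses will be conducted on the full sample (intent to treat analysis"). It names no test or model, covariate, missing-data assumption, imputation rule or sensitivity analysis.
- **Table 1 and the Schedule of Assessments:** IBS-SSS is collected at weeks 0, 4, 8 and 24.
- **Study completion:** "Patients who have completed all of the IBS-SSS at weeks 0, 4, 8, and 24 will be considered completers of the study". This set is not linked to any analysis.

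No other section covers missing outcomes, or says whether patients who stop using the app are still asked for their scores.

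**The concern.** The plan expects some patients to withdraw and promises to analyse everyone, but does not say what happens to a patient whose week-8 score is missing. Someone will have to choose a rule, and nothing requires the choice to be made before the data are seen. The simplest choice is to drop those patients. That departs from the full-sample promise, and it favours Zemedy if patients who do badly are the ones who leave that arm.

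The plan also passes over information it is already paying for. The baseline score enters only by subtraction, if change is what is compared, and the week-4 score has no stated role in the week-8 result. In a trial of 22 to 30 per arm, both can sharpen the estimate at no cost in patients or visits.

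**Working it through.** **1. The plan's own figure.** Inputs from the Power section are 22 per arm, 80% power, alpha 0.05 and 50 points. Without an SD, the 22 cannot be checked independently; it can only be solved backwards. For a two-sided two-sample t-test (noncentral t), 22 per arm detects a standardised difference of 0.865 with 80% power. The implied SD is 50 / 0.865 = 57.8 (65.6 if one-sided). I take the 80% as given, read the 50 points as a between-arm difference, and use 57.8 for scale only.

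**2. The withdrawal allowance.** 1 − 22/30 = 0.267, or 8 of 30. This is inferred. A 25% allowance also rounds up to 30 (22/0.75 = 29.3), while 20% gives 28 and 30% gives 32. It covers withdrawal over a 24-week trial, so putting all of it before week 8 is the worst case.

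**3. The estimate depends on the missing-data rule.** Suppose 8 of 30 per arm are lost, the true difference is 50 points, half of it is present at week 4, and leavers share the benefit:
- complete case: 50;
- week-4 score carried forward: 50 × 22/30 + 25 × 8/30 = 43.3;
- baseline carried forward: 50 × 22/30 = 36.7.

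Power under the three rules is almost the same (simulation, 8,000 runs, correlation 0.5: 0.798, 0.805 and 0.780). The rule changes the size of the reported effect more than the chance of significance. With no true effect, taking the most favourable of the three rules after seeing the data raises the 5% error to about 7% (simulation, 20,000 runs per correlation).

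**4. Bias from dropping patients.** Assume no true difference, Zemedy leavers 50 points worse than Zemedy stayers, TAU leavers no different from TAU stayers, equal loss w in both arms, and SD 57.8. The false difference is w × 50.

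| Loss by week 8 | Left per arm | False difference | False-positive rate |
|---|---|---|---|
| 10% | 27 | 5.0 | 6% |
| 20% | 24 | 10.0 | 9% |
| 26.7% | 22 | 13.3 | 12% |

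**5. What a missing-at-random model can and cannot do here.** If leavers look like stayers at weeks 0 and 4, the model has nothing to correct with, and the 13.3 points remain. If they are already 25 points worse at week 4, and all pairs of visits correlate 0.5, the regression weight on week 4 given baseline is 0.5 / 1.5 = 1/3. The correction is then 25 × 1/3 × 0.267 = 2.2 points. Informative withdrawal therefore needs a separate sensitivity analysis and, better, actual follow-up scores.

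**6. What baseline adjustment gains.** Let r be the correlation of baseline with week 8 (assumed). If 57.8 is the SD of change, the adjusted SD is 57.8 × √((1 + r)/2). If it is the SD of the week-8 score, the adjusted SD is 57.8 × √(1 − r²). Power for 50 points at 22 per arm:

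| r | SD is of change | SD is of week-8 score |
|---|---|---|
| 0.3 | adjusted SD 46.6, about 93% | 55.2, 84% |
| 0.5 | 50.1, 90% | 50.1, 90% |
| 0.7 | 53.3, 86% | 41.3, about 97% |

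Power is above 80% in every cell. Any further gain from the week-4 scores of leavers is not counted.

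**The case against.** The strongest reply is that nothing here is contradictory. Enrolling extra patients so that enough remain with data is normal practice and fits an intent-to-treat analysis once a method is named. That is right. A reader might infer that the Power and Statistical evaluation sections describe two conflicting analyses, or that dropping leavers is the only reading that matches the 22. Neither follows: a missing-at-random analysis of all randomised patients keeps both 22 and 30 unchanged.

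Three further limits also stand.
- The 8 of 30 is not a stated rate, and loss by week 8 may be well below it.
- The 50 points is used to size the trial. No section makes it a threshold the estimate must reach, so the spread of 50, 43 and 37 is not a matter of passing or failing.
- The Statistical evaluation wording, which mentions comparison between evaluation points, can be read as change. It should not be set against the Primary Endpoint as a different outcome.

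It can also be said that the particular model is a preference, since any prespecified rule would close the gap. That holds for the missing-data rule alone. It does not answer the gain from baseline adjustment, which a simple rule such as dropping leavers or carrying scores forward would not bring.

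**Conclusion.** The point holds as an omission with a readily available improvement, and it should be fixed before unblinding. The plan promises a full-sample comparison without saying how patients with no week-8 score are included, and as described it neither adjusts for baseline nor uses week 4.

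The size rests on assumptions. The false 5 to 13 points needs withdrawal that is informative in the Zemedy arm only, with leavers 50 points worse, and its upper end needs the whole inferred allowance to be lost by week 8. The gain to about 84–97% power at 22 per arm needs an assumed correlation of 0.3 to 0.7 and depends on which SD lies behind the stated 80%.

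A reader might also conclude that the trial is underpowered. The documents do not support that: the 80% at 22 per arm is not disputed, and loss by week 8 and outcomes in leavers are unknown. The existence of the gap depends on none of these figures.

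**What to change.** **Statistical evaluation, add:**

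> Primary analysis: all randomised patients in the arm assigned. IBS-SSS at weeks 4 and 8 is analysed in a mixed model for repeated measures with arm, week, arm-by-week and baseline IBS-SSS. The primary result is the arm difference at week 8, with missing scores handled as missing at random. Sensitivity analysis: missing Zemedy scores are multiply imputed from the TAU arm. IBS-SSS is requested at weeks 4, 8 and 24 from every randomised patient who has not withdrawn consent, including those no longer using the app. Both analyses are fixed before unblinding.

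With baseline as a covariate, the arm difference in week-8 score equals the arm difference in change, so the primary endpoint is unchanged.

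**Power:** say that 22 per arm is the number with week-8 data. It would also help to give the SD and say whether it is that of change or of the week-8 score.

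**Cost:** no new patients or visits, because the scores are already scheduled. It does require a protocol amendment with IRB review, and requesting scores from patients who have stopped using the app needs some follow-up effort. The sensitivity result may be less favourable: if Zemedy leavers in truth had no benefit, a 50-point difference would become 50 × 22/30 = 36.7 points at the worst-case loss, or 45 points at 10% loss.
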